7.2.1 Definition of derived variables

Definition of Baseline

Unless otherwise specified, the baseline value will be taken as the last non-missing value available prior to the start of dosing with teplizumab.

Definition of Study Day

In data listings, the day of the first dose of teplizumab administration will be designated Study Day 1. The day before the day of the first dose of teplizumab administration will be designated Study Day -1.

Body Mass Index

Body mass index (BMI) is calculated using the formula:

$$BMI \left(\frac{kg}{m^2} \right) = \frac{weight(kg)}{[height(m) \cdot height(m)]}$$

Body Surface Area

Body Surface Area (m²) is calculated using the Mosteller formula:

$$BSA(m^2) = \sqrt{\frac{[Height(cm) \times Weight(kg)]}{3600}}$$

7.2.2 Imputing missing values

In general, missing values will not have any imputation, with some exceptions noted below:

Adverse Events, Prior Medications and Concomitant Medications

Partial dates for adverse event start/stop or concomitant medication start/stop will not be imputed in data listings. However, information from partial adverse event start dates may be used to determine whether an adverse event is treatment emergent. Information from partial start dates may be used to determine between prior medications and concomitant medications.

7.3 Disposition of participants

The number of participants enrolled will be tabulated as well as the number and percentage of enrolled participants who are in the Safety, PK, and Immunogenicity analysis sets.

The number and percentage of participants in the Safety analysis set who discontinue study drug early and reason for early discontinuation of study drug [adverse event, Investigator decision, participant decision, other] will be tabulated.

The number and percentage of participants in the Safety analysis set who discontinue the study early and complete the study will be tabulated along with reasons for early study discontinuation [lost to follow-up, withdrawal of consent/assent, death, Investigator or Sponsor judgement, pregnancy, other].

Disposition of participants will be provided in a separate data listing which will include information about informed consent/assent. Additional data listings will detail inclusion/exclusion criteria not met and protocol deviations in the Safety analysis set.

7.4 Demographic and baseline characteristics and medical history

The following demographic and baseline characteristics (including disease characteristics) will be summarized on the Safety analysis set:

- Age at screening (years)
- Sex
- Ethnicity
- Race
- Height (cm)
- Weight (kg)
- Body Mass Index (kg/m²)
- Body Surface Area (m²)
- Type of positive T1D-related autoantibody (GADA, IA-2, mIAA, ZnT8)
- Number of positive autoantibodies (1,2,3,4)
- Time from T1D diagnosis to first dose of teplizumab in TN-10 Extension (weeks)

Time from T1D diagnosis to first dose of teplizumab in TN-10 Extension will be calculated as (Date of first dose of teplizumab in TN-10 Extension – Date of T1D diagnosis)/7.

Demographic and baseline characteristics will also be provided in data listings for the Safety analysis set. This listing will include a calculation of Time from TN-10 trial treatment start to T1D diagnosis (months), calculated as (Date of T1D diagnosis – Date of first dose of teplizumab in TN-10 trial + 1)/30.4375.

Medical history will be coded using the latest version of the Medical Dictionary for Regulatory Authorities (MedDRA) applicable at the time of database lock. A data listing of medical history by participant will be provided for the Safety analysis set.

7.5 Prior and concomitant medications

Prior and concomitant medications will be coded using the latest version of the WHO Drug dictionary applicable at the time of database lock. Prior medications are those which start and stop before the first dose of study treatment. Concomitant medications are those which start before study treatment and continue into the study treatment period as well as medications which start after the first dose of study treatment is administered.

A data listing of medications will be provided for the Safety analysis set with a designation of whether a medication is prior or concomitant. If there is not enough available data to make this designation, a medication will be assumed to be both prior and concomitant.

7.6 Extent of exposure and compliance

Extent of exposure will be summarized for the Safety analysis set showing:

- Number of participants dosed with teplizumab at each visit
- Number of doses received per participant
- Descriptive statistics of follow up time (years) and total follow up time (person-years)
- Cumulative total teplizumab dose (μ g) in TN-10 Extension study
- Received prior teplizumab treatment in TN-10 trial (Yes, No)
 - Time between last teplizumab exposure in TN-10 trial and first teplizumab dose in TN-10 Extension study (months) [in subjects receiving teplizumab in TN-10 trial]
- Cumulative total teplizumab dose (μ g) in TN-10 and TN-10 Extension study

Follow up time (years) per participant will be calculated as (Date of end of study participation – date of first dose of teplizumab in TN-10 Extension + 1)/365.25.

Time between last teplizumab exposure in TN-10 trial and first teplizumab dose in TN-10 Extension study (months) will be calculated as (Date of first teplizumab dose in TN-10 Extension study – date of last dose of teplizumab in TN-10 trial)/30.4375.

Extent of exposure will also be provided in a data listing. The listing will include any relevant information about dose slowing, interruptions, or discontinued dosing administrations. A separate listing will also provide an exposure summary from TN-10 and the TN-10 Extension study for each TN-10 Extension participant.

7.7 Analysis of safety and tolerability

All safety analyses will be performed based on the Safety analysis set.

7.7.1 Adverse events

Adverse events will be coded using the latest version of MedDRA applicable at the time of database lock.

A treatment emergent adverse event (TEAE) is defined as an adverse event which starts during or after the first dose of teplizumab. If an adverse event occurring the same day as the first dose of teplizumab cannot be determined to occur before or after the dosing begins, it will be assumed to be treatment emergent.

Adverse event severity is assigned according to the National Cancer Institute CTCAE v5.0. In the case of summaries by CTCAE grade, the highest grade experienced by the participant will be used for the reporting category.

Relationship of an adverse event to study treatment will be considered as "Related" in tabular summaries if the options of "Possible", "Probable", or "Definite" are selected for the adverse event in the eCRF. Options of "Unrelated" or "Unlikely" will be considered as "Not Related".

An adverse event is defined as an Adverse Event of Special Interest (AESI) if it meets any of the following criteria:

- All \geq Grade 3 infections (includes all opportunistic infections): viral, fungal, bacterial
- Acute mononucleosis-like illness (e.g., fever, pharyngitis, lymphadenopathy, clinical EBV and CMV infections and reactivations)
- Malignancies including lymphomas
- Severe hypoglycemic episodes
- \geq Grade 3 liver function abnormalities (AST, ALT, bilirubin), i.e., an AST or ALT value $>5.0 \times$ ULN or a bilirubin value $>3.0 \times$ ULN
- \geq Grade 3 thrombocytopenia (platelet counts less than 50,000/ μ L)
- \geq Grade 3 neutropenia (<1000 PMN/ μ L on 2 consecutive evaluations performed on different days)
- \geq Grade 4 allergic/hypersensitivity reaction (anaphylaxis)
- \geq Grade 3 Rash
- \geq Grade 4 cytokine-release syndrome
- Lymphocyte count $<500/\text{mm}^3$ for 7 days or longer

Table 2 The Search Criteria for AESI

AESI	Search Criteria
\geq Grade 3 infections (will include all opportunistic infections)	SOC – 'Infections and Infestations'; \geq Grade 3
Acute mononucleosis-like illness (e.g., fever, pharyngitis, lymphadenopathy)	PT – 'Mononucleosis syndrome', 'Epstein-Barr virus antibody positive', 'Epstein-Barr virus test positive', 'Epstein-Barr viremia', 'Cytomegalovirus antibody positive', 'Cytomegalovirus test positive', 'Infectious mononucleosis', 'Lymphadenopathy', 'Epstein-Barr virus infection', and 'Cytomegalovirus infection'
Lymphomas or other malignancies	SOC – 'Neoplasms benign, malignant and unspecified (incl cysts and polyps)' and HLT – includes 'malignant' or 'lymphomas' or 'benign'

Severe hypoglycemic episodes	PT – 'Hypoglycaemic seizure', 'Hypoglycaemic coma', 'Hypoglycaemic unconsciousness' of any grade; PT – 'Hypoglycaemia' of ≥ Grade 3
≥ Grade 3 liver function abnormalities (aspartate aminotransferase [AST], alanine aminotransferase [ALT], bilirubin) i.e., an AST or ALT value >5.0x upper limit of normal (ULN) or a bilirubin value >3.0x ULN	PT – 'Alanine aminotransferase increased', 'Aspartate aminotransferase increased', 'Blood bilirubin increased', 'Liver function tests increased', 'Hypertransaminasemia', 'Transaminase elevation', 'Hyperbilirubinemia'; ≥ Grade 3
≥ Grade 3 thrombocytopenia (platelet counts less than 50,000/µL)	PT – 'Thrombocytopenia'; ≥ Grade 3
≥ Grade 3 neutropenia (<1000 polymorphonuclear leukocytes [PMN]/µL) on 2 consecutive evaluations performed on different days	PT – 'Neutropenia'; ≥ Grade 3
≥ Grade 4 allergic/hypersensitivity reaction, i.e., anaphylaxis	PT – 'Dermatitis allergic', 'Drug hypersensitivity', 'Anaphylactic reaction', 'Immune reaction', 'Anaphylaxis', 'Hypersensitivity', 'Infusion related reaction', 'Serum sickness'; ≥ Grade 4
≥ Grade 3 rash	SOC – 'Skin and subcutaneous tissue disorders'; ≥ Grade 3
≥ Grade 4 cytokine-release syndrome, i.e., life-threatening; pressor or ventilatory support indicated	PT – 'Cytokine release syndrome'; ≥ Grade 4
Lymphocyte count <500 mm ³ for 7 days or longer	PT – 'Lymphopenia'; ≥ Grade 3; at least 7 days

SOC = system organ class; PT = preferred term; HLT = high level term

Note: Nasopharyngitis, Pharyngitis, pharyngitis streptococcal should not be included in search criteria.

Summary Tables

An overall summary table of treatment emergent adverse events will display the number and percentage of participants with at least one

- TEAE
- TEAE related to study treatment
- TEAE leading to study treatment discontinuation
- TEAE leading to study discontinuation
- TEAE leading to death
- TEAE by CTCAE grade
- TEAE of special interest (AESI)
- Serious TEAE
- Serious TEAE related to study treatment

Summary tables will be produced which display the number and percentage of participants having at least one of the following categories by MedDRA System Organ Class (SOC) and Preferred Term (PT):

- TEAE
- TEAE related to study treatment
- TEAE leading to study treatment discontinuation
- TEAE leading to study discontinuation
- Serious TEAE
- Serious TEAE related to study treatment

Summary tables will be produced by descending frequency of MedDRA Preferred Term (PT) for the following categories:

- TEAE

A summary table will be produced by AESI category (defined in [Table 2](#)) and MedDRA Preferred Term for the following category:

- TEAE of special interest (AESI)

Participants with more than one TEAE in each SOC or PT will only be represented once per row in these summary tables by SOC and/or PT.

Data Listings

The following data listings for adverse events will be produced:

- TEAE
- Adverse events which are not treatment emergent
- TEAE leading to study treatment discontinuation
- TEAE leading to study discontinuation
- TEAE leading to death
- TEAE of special interest (AESI)
- Serious TEAE

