8.4.1.1. Time Period and Frequency for Collecting AE and SAE Information

All AEs will be collected from the signing of the informed consent form (ICF) until the follow-up visit at the time points specified in Section 1.3.

All SAEs will be recorded and reported to the sponsor or designee immediately and under no circumstance should this exceed 24 hours, as indicated in Appendix 3 in Section 10.3. The investigator will submit any updated SAE data to the sponsor within 24 hours of it being available.

Investigators are not obligated to actively seek AE or SAE after conclusion of the study participation. However, if the investigator learns of any SAE, including a death, at any time after a participant has been discharged from the study, and he/she considers the event to be reasonably related to the study intervention or study participation, the investigator must promptly notify the sponsor.

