10.3.1. Definition of AE

AE Definition

- An AE is any untoward medical occurrence in a patient or clinical study participant, temporally associated with the use of study intervention, whether or not considered related to the study intervention.
- NOTE: An AE can therefore be any unfavorable and unintended sign (including an abnormal laboratory finding), symptom, or disease (new or exacerbated) temporally associated with the use of study intervention.
- Hypoglycemia and hyperglycemia will be reported as adverse events only in the case of requiring the assistance of others due to loss of consciousness or diabetic ketoacidosis (DKA).

Unexpected AE:

- An adverse event is considered unexpected when the nature (specificity) or severity of the event is not consistent with the risks described in the Investigator's Brochure or the informed consent document.

Events Meeting the AE Definition

- Any abnormal laboratory test results (hematology, clinical chemistry, or urinalysis) or other safety assessments (e.g., ECG, radiological scans, vital signs measurements), including those that worsen from baseline, considered clinically significant in the medical and scientific judgment of the investigator (i.e., not related to progression of underlying disease).
- Exacerbation of a chronic or intermittent pre-existing condition including either an increase in frequency and/or intensity of the condition.
- New conditions detected or diagnosed after study intervention administration even though it may have been present before the start of the study.
- Signs, symptoms, or the clinical sequelae of a suspected drug-drug interaction.
- Signs, symptoms, or the clinical sequelae of a suspected overdose of either study intervention or a concomitant medication. Overdose per se will not be reported as an AE/SAE unless it is an intentional overdose taken with possible suicidal/self-harming intent. Such overdoses should be reported regardless of sequelae.

Events NOT Meeting the AE Definition

- Any clinically significant abnormal laboratory findings or other abnormal safety assessments which are associated with the underlying disease, unless judged by the investigator to be more severe than expected for the participant's condition.
- The disease/disorder being studied or expected progression, signs, or symptoms of the disease/disorder being studied, unless more severe than expected for the participant's condition.

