- Medical or surgical procedure (e.g., endoscopy, appendectomy): the condition that leads to the procedure is the AE.
- Situations in which an untoward medical occurrence did not occur (social and/or convenience admission to a hospital).
- Anticipated day-to-day fluctuations of pre-existing disease(s) or condition(s) present or detected at the start of the study that do not worsen.

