10.3.4. Reporting and Follow-Up of AE and/or SAE

AE and SAE Reporting

Timely, accurate, and complete reporting and analysis of safety information from clinical studies are crucial for the protection of participants, Investigators, and the Sponsor, and are mandated by regulatory agencies worldwide. The Sponsor has established Standard Operating Procedures in conformity with regulatory requirements worldwide to ensure appropriate reporting of safety information; all clinical studies conducted by the Sponsor or its affiliates will be conducted in accordance with those procedures.

The determination of seriousness, severity and causality must be made by the physician Investigator who is qualified to review adverse event information, provide a medical evaluation of adverse events, and classify adverse events based upon medical judgment.

An adverse event is any untoward medical occurrence in a clinical study participant from the time they formally agree to participate in the study (eg, by providing informed consent/assent) through their last study contact (eg, last visit or status update). An adverse event does not necessarily have a causal relationship with the study drug. An adverse event can therefore be any unfavorable and unintended sign (including an abnormal finding), symptom, or disease temporally associated with the use of a study drug (investigational or non-investigational product), whether or not related to that study drug (investigational or non-investigational product).

This includes any occurrence that is new in onset or aggravated in severity or frequency from the baseline condition, or abnormal results of diagnostic procedures, including laboratory test abnormalities.

A treatment-emergent adverse event (TEAE) is defined as an AE that occurs after the first dose of study drug administration (Day 1) through the end of the study or early termination.

The Investigator must follow all SAEs (including serious AESIs) until resolution even if this extends beyond the study-reporting period. Resolution of a SAE is defined as the return to pre-treatment status or stabilization of the condition with the expectation that it will remain chronic. At any time after completion of the study, if an Investigator becomes aware of a serious adverse event that s/he suspects is related to study drug, the Investigator should report the event to the Pharmacovigilance contact.

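### The treatment-emergent flag uses start date alone, so an adverse event that begins before first dose and worsens on teplizumab can miss the safety tables, depending on how the site records it

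*SAP*

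**What the plan says.** SAP 7.7.1 gives the rule as "A treatment emergent adverse event (TEAE) is defined as an adverse event which starts during or after the first dose of teplizumab". The only refinements also concern start: an event on Day 1 whose order relative to dosing is unclear is assumed treatment emergent, and SAP 7.2.2 allows partial start dates to inform the flag.

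All the adverse event summary tables in SAP 7.7.1 are built on TEAEs, including those for AESIs, serious events and CTCAE grade. The remaining events go to a listing titled "Adverse events which are not treatment emergent".

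Protocol 8.4.1.1 starts collection at consent, and Protocol 4.1 allows up to 4 weeks of screening. Protocol 10.3.4 counts as an adverse event "any occurrence that is new in onset or aggravated in severity or frequency from the baseline condition", and Protocol 10.3.1 includes "Exacerbation of a chronic or intermittent pre-existing condition including either an increase in frequency and/or intensity of the condition". The TEAE sentence in Protocol 10.3.4 refers to an event occurring after the first dose and, like the SAP, has no separate worsening clause.

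**The concern.** The primary endpoint is the incidence of TEAEs, AESIs and SAEs. A flag driven by start date does not see a change in grade or seriousness in an event that was already open at first dose. Three features of this plan make that relevant.

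- Seven of the eleven AESI categories in SAP 7.7.1 are named by a Grade 3 or Grade 4 threshold. A rise in grade is how an existing mild event would enter them.
- The endpoint names SAEs, but the SAP tabulates and separately lists only serious TEAEs. An event that starts before dosing and becomes serious afterwards could miss both outputs.
- Laboratory results and vital signs are presented as listings only (SAP 7.7.2 and 7.7.3), so no summary table elsewhere would show the worsening.

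Any misclassification of this kind runs one way, towards too few events. The SAP's tie-break for Day 1 leans the other way, so a worsening clause would fit its evident intent.

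**Working it through.** The plan gives no figure to reproduce, and the study is descriptive with no formal sample size calculation. The check is to apply the definitions to each possible course of an event.

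1. **Condition present before consent, worse after first dose.** Under Protocol 10.3.1 the exacerbation is itself the adverse event. Pre-existing conditions are set aside only as "Anticipated day-to-day fluctuations of pre-existing disease(s) or condition(s) present or detected at the start of the study that do not worsen". The event starts at the worsening, after dosing, so it is a TEAE and is counted.
2. **Event starts between consent and first dose, worsens on treatment, and the worsening is entered as a new event.** Protocol 10.3.4 supports this, since aggravation from baseline is an adverse event. The new record starts after dosing, so it is a TEAE and is counted.
3. **Same course, but the site raises the grade or seriousness on the existing record.** The start date remains before dosing. The event is not a TEAE and appears only in the listing of non-emergent events. The SAP rule of reporting a participant's highest grade does not help, because the record never enters the TEAE summaries.
4. **Event starts on Day 1, order unclear.** The tie-break makes it a TEAE.

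Only course 3 is lost from the tables. Nothing in either document chooses between courses 2 and 3. Protocol 8.4.1.3 requires each event to be followed at later visits until it resolves or stabilises, which is compatible with updating the original record.

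**Which events could follow course 3.** Protocol 5.2 excludes, at screening or before first dose, lymphocytes below 1000/µL, neutrophils below 1500/µL, platelets below 150,000/µL, hemoglobin below 10 g/dL, AST or ALT above 1.5 x ULN, chronic active infection (localized skin infection excepted) and acute EBV or CMV infection. Protocol 10.3.1 makes a laboratory abnormality an adverse event only if judged clinically significant. A mild acute infection or a rash open at first dose is what plausibly remains.

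**Size.** One participant whose only qualifying event in a row is misclassified changes that row by 1/N.

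- N = 30 (the maximum in SAP 6): 1/30 = 3.3 percentage points.
- N = 20 (assumed): 1/20 = 5.0 points.
- N = 10 (assumed): 1/10 = 10.0 points.

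The two smaller values are assumptions. SAP 7.10 says only that few participants enrolled.

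**The any-TEAE row.** In TN-10, Table 1 of Protocol 2.3 places 23 + 20 = 43 of 44 teplizumab participants (97.7%) at Grade 2 or 3 for drug-related events. If this study is similar, nearly every participant will have some other TEAE, so one misclassified event would leave that row unchanged.

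**The case against.** The strongest reply is that the protocol already makes worsening an adverse event in its own right. SAP 1 describes the SAP as a supplement to the protocol, and SAP 7.10 declares no change to that definition. Recorded accordingly, the worsening starts after dosing and satisfies the SAP rule. Protocol 10.1.9 also promises CRF completion guidelines, which may deal with worsening and are not in the documents. This stands against a stronger reading that a reader might infer, namely that any event present at screening that worsens is omitted. The documents do not support that: courses 1 and 2 are counted. The reply does not close course 3, because it depends on an instruction that neither document contains.

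A reader might also infer that the SAP narrowed the protocol's definition. It did not; the protocol's TEAE sentence lacks the clause too.

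Two further points stand in part. Cytopenia is a weak example, because the exclusion criteria remove most of it, although milder abnormalities can pass. And no event disappears from the report: the non-emergent events are listed, the study has one arm and at most 30 participants, and such a listing can be read case by case. A listing is still not the incidence that the primary endpoint names.

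**Conclusion.** The concern holds in a limited form. Under the stated rule, an adverse event that starts between consent and first dose and then rises in grade or becomes serious can be left out of the TEAE, AESI and serious-TEAE tables. Whether it is depends on how the site enters the worsening, which the documents leave open. Both documents share the gap.

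The number affected is unknown and may be zero. The 3.3 points at N=30 (5 or 10 points at an assumed N of 20 or 10) is the most that one participant can move a single row, and only if that participant has no other event in it. It is not an estimate of bias in overall TEAE incidence. The conclusion assumes that at least some sites would update an open record, which the documents neither confirm nor rule out.

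**What to change.** In SAP 7.7.1, define a TEAE as an adverse event that starts during or after the first dose, or that starts before it and increases in CTCAE grade or becomes serious on or after it. Keep the Day 1 tie-break.

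The clause can be programmed only if the CRF holds grade and seriousness with dates before and after dosing, which the documents do not show. Where it does not, instruct sites to record the worsening as a new event dated at the worsening, and check the listing of non-emergent events for such cases before the tables are final. The instruction would also cover an increase in frequency without a change of grade, which the protocol counts as an adverse event but a grade comparison would miss.

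The cost is one sentence, a small amount of programming and possibly a CRF-completion instruction. If no such case exists, no table changes.

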2.3. Safety Experience with Teplizumab

Much of the safety experience with teplizumab are in Stage 3 T1D individuals. In the Protégé and other clinical studies, teplizumab is generally very well tolerated. In general, there are no major differences in overall adverse events (AEs) of clinical concern and serious adverse events (SAEs) between teplizumab and placebo groups. The most common AEs associated with teplizumab are a decrease in white blood cell counts, nausea and/or vomiting, upper respiratory infections or nasopharyngitis and elevations in AST or ALT and anemia, all usually mild or moderate. The most frequent observation is a decrease in white blood cell count (WBC), including, in order, transient lymphopenia, leukopenia, and neutropenia. Transient lymphopenia has occurred in ~2/3 of teplizumab recipients and is usually mild or moderate, which is consistent with teplizumab’s mechanism of action (Sherry 2011, Hagopian 2013). These events are usually self-limited and occur with teplizumab dosing and spontaneously reconstitute. For example, lymphocytes return to 80% of baseline levels within approximately 14 days of dosing. Approximately half of those who receive teplizumab develop a mild rash, sometimes pruritic, during dosing cycles, which spontaneously resolves within 7-14 days. Due to its mechanism of action, cytokine release syndrome is a potential concern with teplizumab dosing but occurs in <10% of teplizumab-treated individuals (for example ~6% in the Protégé study) and is usually mild-to-moderate and well

tolerated. Prophylactic administration of non-steroidal anti-inflammatory drugs (NSAIDs; eg, ibuprofen) and antihistamines (eg, diphenhydramine) appear to reduce the occurrence and the severity of its signs and symptoms significantly.

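### Three search cells in SAP Table 2 (malignancy, neutropenia, rash) do not implement the AESI criteria they stand for, so events that fail the written definition can enter a component of the primary endpoint

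*SAP*

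**What the plan says.** SAP section 2 names AESI incidence, with TEAEs and SAEs, as the primary endpoint. SAP 7.7.1 lists the criteria that make an adverse event an AESI, and Table 2 then gives each criterion a search rule. The AESI summary is by category and preferred term (PT), with the categories taken from Table 2. SAP 7.8.5 also treats Table 2 as the AESI definition.

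- **Malignancy.** The criterion is "Malignancies including lymphomas" and the row label is "Lymphomas or other malignancies". The search is the neoplasm system organ class (SOC) with a high level term (HLT) that "includes 'malignant' or 'lymphomas' or 'benign". There is no grade limit.
- **Neutropenia.** The criterion and the row label both require Grade 3 or higher, with fewer than 1000 PMN/µL, "on 2 consecutive evaluations performed on different days". The search cell reads "Neutropenia'; ≥ Grade 3" and stops there.
- **Rash.** The criterion and the label are Grade 3 or higher rash. The search is the whole SOC: "Skin and subcutaneous tissue disorders'; ≥ Grade 3".

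SAP 7.10 declares that the SAP's AESI definition differs from the protocol's and aligns with one agreed for the Integrated Summary of Safety (ISS). It does not mention any difference between the SAP's criteria and the SAP's searches.

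**The concern.** A definition and the search that implements it should select the same events. Here a programmer who follows the search cells and one who follows the criteria, or the row labels, can get different counts from one signed plan. Followed literally, the searches could put a benign lesion under a malignancy heading, an unconfirmed low neutrophil count under a heading that says it was confirmed, and a non-rash skin event under rash.

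The confirmation condition is not idle. Protocol 2.3 lists the white-cell falls after teplizumab as "in order, transient lymphopenia, leukopenia, and neutropenia" and describes them as usually self-limited. A requirement for a second low count would be expected to filter short falls of that kind.

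Because the study is descriptive, the reported count is itself the primary result. No test or model stands between a misclassified event and the figure in the report.

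**Working it through.** **Step 1. Compare criterion and search, row by row.**

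| Row | Criterion (SAP 7.7.1) | Search cell (Table 2) | What the search adds |
|---|---|---|---|
| Malignancy | malignant disease, including lymphoma | HLT containing malignant, lymphomas or benign | benign neoplasms, any grade |
| Neutropenia | Grade 3 or higher, two consecutive evaluations on different days | PT Neutropenia, Grade 3 or higher | events without a second low count |
| Rash | Grade 3 or higher rash | skin SOC, Grade 3 or higher | Grade 3 or higher skin events that are not rash |

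**Step 2. Does Table 2 leave such conditions to the label by convention?** No. The lymphopenia cell carries its time condition in the search: "Lymphopenia'; ≥ Grade 3; at least 7 days". So the table writes a condition into the search cell in at least one row, and its absence from the neutropenia cell cannot be read as a shared convention.

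**Step 3. Value of one participant.** There is no planned AESI rate or precision figure to reproduce: SAP section 6 says the sample size has no formal statistical basis. One participant is worth 100/n percentage points.

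- n=33 (maximum in Protocol 9.2): 100/33 = 3.0
- n=30 (maximum in SAP section 6): 100/30 = 3.3
- n=20 (assumed): 100/20 = 5.0
- n=10 (assumed): 100/10 = 10.0

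The last two sizes are assumptions, because SAP 7.10 says that few were enrolled without giving the number. The category row moves by this amount. The overall at-least-one-AESI figure moves by it only if the participant has no other AESI.

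**Step 4. Could the two-evaluation condition simply be enforced?** As the Schedule of Events reads, blood counts fall on Days 1, 2, 3, 4, 6, 8, 28, 84, 364 and 546. A low count first seen on Day 8 has its next scheduled count 28 − 8 = 20 days later. From Day 28 the gap is 84 − 28 = 56 days. Protocol 6.2 and 7.1 call for laboratory review on each dosing day, which may supply extra counts up to Day 12, but there is no equivalent in follow-up. Dropping every event without a second low count would therefore also drop events that nobody re-measured.

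**The case against.** The strongest reply is that this is labelling. No inference is planned (SAP 7.2). The AESI table shows preferred terms under each category, so a benign or non-rash term can be seen in its row. AESIs and neutrophil values are listed, and with at most about 30 participants case-level checking is easy. The neutropenia label does state the two-evaluation condition. The searches may also have come from the ISS with the definition. Most of this stands, and it is why the point is minor. It does not remove the contradiction: SAP 7.10 covers only SAP against protocol, and the documents do not show where the search strings came from.

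A reader might go further and infer that AESI incidence will be over-stated overall. The documents do not support that. The neutropenia row rests on a single PT, whereas the liver row lists several, so a qualifying event coded elsewhere would be missed. The HLT word match could also miss a malignancy. The mononucleosis row works in the other direction too: its criterion gives fever and pharyngitis as examples, but the search has no fever term and the table note excludes pharyngitis.

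A reader might also look for a rate in TN-10. There, 20 of 44 teplizumab participants had Grade 3 as their worst drug-related grade. Fifteen (15/44 = 34.1%) involved early lymphopenia, which leaves 5 of 44 (11.4%). This is not a misclassification rate. It covers drug-related events only, in Stage 2 participants on a 14-day course. It is not split by type, and it would include true rash and confirmed neutropenia. For rash, drug-related skin events affected 16/44 = 36.4% and rash is given as 36%, which gives no sign of many extra events.

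Finally, Protocol 7.2 names dry skin and nail changes at Grade 3 or higher, but as exceptions to a discontinuation rule. It does not forecast them.

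**Conclusion.** The inconsistency is certain on the current text: three search cells do not implement the SAP's own criteria or their own row labels, in a component of the primary endpoint. Followed as written, they can count events that fail the written definition.

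The size cannot be stated as a rate, and the net direction for total AESI incidence is open. What can be stated is the value of one misclassified participant: 3.3 points at the SAP maximum of 30, rising to 10.0 points if only 10 are enrolled (assumed). TEAE and SAE totals are unaffected. Severity is minor.

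**What to change.** In SAP Table 2:

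1. **Malignancy.** Delete *benign* from the search, or relabel the row as all neoplasms.
2. **Rash.** Restrict the search to named rash PTs, or relabel the row as Grade 3 or higher skin disorders.
3. **Neutropenia.** Keep every PT Neutropenia event of Grade 3 or higher in the table. Flag each as confirmed, not confirmed on repeat, or not re-measured, using the neutrophil values already listed under SAP 7.7.2. Change the row label to match. Excluding events with no repeat would under-count, given the gaps in step 4.

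If the searches were inherited from the ISS, keep them, state that Table 2 governs, and relabel the three rows to say what they capture.

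The cost is a few lines of SAP text and a small amount of programming. Narrowing the searches, rather than relabelling, would lose some comparability with the ISS if the searches came from it.
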